4.2 Study Design

This is a two-phase study and comprises a shorter feasibility phase followed by a larger RCT.

Feasibility Phase

This is a prospective, single-arm study, in free-living conditions in young children with T1D on insulin pump therapy. Participants will have a 2-week run-in phase (± 1 week) during which participants will use the system in Manual Mode followed by a 6-week study phase (± 1 week) during which SmartGuard is enabled. The study duration is for 8 weeks (± 2 weeks).

The study design is as shown in the Figure 1 as below.

[figure not shown]

Figure 1: Feasibility phase design

Study Device

Participants will use the investigational study device. The target glucose set point will be initially set at 6.7mmol/l. This will be reviewed weekly by the research doctor. If there is no significant hypoglycaemia (< 4% below 3.9 mmol/l and < 1% below 3.0 mmol/l) and there is scope to improve time in range, the target will be revised to 5.5mmol/l. The active insulin time will be set at 4 hours at commencement and adjusted as required.

VISIT 1 (2 to 3 hours)

(Eligibility Confirmation, Baseline data collection, Pump training).

Participants will be checked if they meet the inclusion criteria listed below in Section 5.2. The following data will be recorded:

Visit 1

1. Consent signed by parent and investigator
2. Auxology
 - a. Height
 - b. Weight
 - c. BMI
3. Demographic
 - a. Date of Birth
 - b. Gender
4. Diabetes clinical

- a. Date of diagnosis
 - b. Current pump/CGM therapy
 - c. HbA1c
 - d. History of severe hypoglycaemia – coma or convulsion or episodes requiring third party assistance (events in last 12 months).
 - e. History of diabetic ketoacidosis (DKA) in the last 12 months
 - f. Hospital admissions in the last 12 months (DKA, Hyperglycaemia, Hypoglycaemia, Non diabetes related)
 - g. Total daily dose of insulin (mean of previous 7 days)
 - h. Co-morbidities and medications
5. Record/review pump settings and review download capability.
 6. Review hypoglycaemia/hyperglycaemia management
 7. Pump training

Parents will be trained on how to use the Medtronic 780G insulin pump. They will be provided with a compatible meter (which communicates with the pump) along with the glucose strips for the study. Parents will also be instructed on how to upload the pump. At this visit, all participants will be provided with a participant record book. All participants will also be provided with a record book to log hypoglycaemia, hyperglycaemia and technical issues related to the device.

Visit 2: CGM training (1 to 2 hours)

Parents will be instructed on how to link their child's CGM to the Medtronic 780G pump and issued with compatible next generation sensor and transmitter, as well as CGM user guide. Initial low and high alarms will be set at 4.0 mmol/L and 15 mmol/L respectively, although these can be changed according to individual preference. Sensor naïve individuals will have familiarisation phase of 7 to 10 days to get used to wearing a sensor.

Visit 1 and 2 could be combined for participants already on Medtronic pumps/sensors.

Visit 3: Commencement of AHCL (1-2 hours)

Once CGM data has been established for a minimum of 3 to 7 days, participant returns for face-to-face instruction on AHCL use and initiation of 'SmartGuard'. Target glucose will be set at 6.7 mmol/l and active insulin time will be set at 4 hours.

During this visit, the sensor will be replaced to demonstrate sensor warm up and AHCL initiation, and provide an opportunity for those unfamiliar with CGM use to practice a sensor change with supervision. The ability of the family to upload the pump at home will be confirmed.

Visits 4-8: Weekly follow-up

Participants will upload their pump weekly and will also have weekly communication with the research nurse and doctor (face to face or video call) to provide support for the following 6 weeks. The need to adjust target glucose or active insulin time will be reviewed with every visit.

Glucose levels will be remotely monitored continuously 24/7 by both caregivers/parents and study staff via CareConnect app. A default urgent low setting alert will be set at 3 mmol/L and caregivers/parents will be contacted by the study staff if this alert persists for more than 20 minutes (an expected recovery time following hypoglycaemia treatment). Communication can be more often – as per clinical need. Adverse events, if any, will be logged at each visit.

Visit 9: End of feasibility phase

This marks the end of the 6-week study period. Clinical data (HbA1c) along with total daily insulin requirement and pump settings at the end of the study will be collected. Short questionnaire asking for feedback using the 780G pump with SmartGuard, will be given to parents (optional).

[figure not shown]
Wash-out period: There should be a minimum wash-out period of 3 months for participants willing to enrol for the larger RCT. The 3-month period is chosen to minimise the impact of any carry over of glycaemic impact with AHCL into the larger RCT.

Randomized Controlled Trial (RCT) Phase

This is a **prospective multicentre randomised controlled, two-arm unblinded, parallel study** in free-living conditions, in young children with type 1 diabetes on insulin pump therapy. Participants will be randomised in two groups; either the control group (standard therapy) or the intervention group (AHCL). The control group will be participants on continuous subcutaneous insulin infusion (CSII) with or without CGM (continuous glucose monitoring). The study duration is for 3 months. This phase will be conducted at four tertiary paediatric diabetes centres (Perth Children’s Hospital, WA, Westmead Children’s Hospital, NSW, Women’s and Children’s Hospital, SA, and Royal Children’s Hospital, VIC).

AHCL group: Investigational pump for 3 months OR Control group: Standard CSII for 3 months.

The study design is as shown in the Figure 2 as below.

*Visits 2B,2C, 5C, 5D optional if data requirement from blinded CGM not met, Visit 5 Blinded CGM only for control group.

Figure 2: Study design RCT

VISIT 1

(Eligibility Confirmation, Baseline data collection and commencement of run-in period).

Information sheets will be provided in advance to participants who potentially fit inclusion criteria. HbA1c should be available from last clinic visit within 3 months of Visit 1.

Participants will be checked if they meet the inclusion criteria listed below in Section 5.2. The following data will be recorded:

1. Consent signed by parent and investigator
2. Auxology
 - a. Height
 - b. Weight
 - c. BMI
3. Demographic
 - a. Date of Birth
 - b. Gender
4. Diabetes clinical
 - a. Date of diagnosis
 - b. Current pump/CGM therapy
 - c. HbA1c
 - d. History of severe hypoglycaemia – coma or convulsion or episodes requiring third party assistance (events in last 12 months).
 - e. History of diabetic ketoacidosis (DKA) in the last 12 months
 - f. Hospital admissions in the last 12 months (DKA, Hyperglycaemia, Hypoglycaemia, Non diabetes related)
 - g. Total daily dose of insulin (mean of previous 7 days)
 - h. Co-morbidities and medications
5. Psychology measures: Psychological scales will be administered to the parents on an electronic platform . (Questionnaires are included in the appendix)
 - a. Functional health status: Quality of life (QOL) WHO 5(11), EQ5D(12)
 - b. Fear of hypoglycaemia: Hypoglycaemia fear survey Parent(13)
 - c. Diabetes-related distress: Problem Areas in Diabetes PAID-Parent version(14)
 - d. Anxiety: GAD-7(15)
 - e. Sleep quality: Pittsburgh Sleep Quality Index(16)
 - f. Technology acceptance and satisfaction: DTQ(17)
6. Review pump settings and download capability.
7. Insertion of the first blinded sensor (next generation sensor and transmitter) to collect baseline glycaemic data. This constitutes first of the two sensors, each sensor provides data for 7 days. Parents will be instructed to test their children for a minimum 3 to 4x/day using the study meter provided. At this visit, all participants will be provided with the study meter and a participant record book.

VISIT 2

VISIT 2A (7 days after Visit 1)

Insertion of 2nd blinded sensor: Participants will return 7 days after sensor insertion to remove and download the first week of CGM data. The glucometer will be uploaded. A new sensor will be inserted and a fresh transmitter attached.

A total of 2 weeks of blinded sensor is required with at least 10 days of data (18). In participants who do not meet this requirement or if the sensor falls off/removed accidentally, repeat sensors will be offered till a maximum of 4 attempts of data collection (2B, 2C).

Hence, the run-in period duration will be over 2 to 4 weeks.

Visit 2B

1. The blinded sensor is removed
2. Insertion of 3rd blinded sensor (if applicable) and to be removed a week later
3. 24-hour food recall interview (to capture baseline dietary pattern)

Visit 2C Insertion of 4th blinded sensor (if applicable) and to be removed a week later

Participants who do not meet the run-in requirements i.e demonstrate ability to use CGM (in sensor naïve individuals) and/or have insufficient data on blinded CGM will not proceed to randomisation and will be withdrawn from the study.

VISIT 3 (Randomisation)

This visit is the treatment allocation visit (see section 4.4 for details).

The following data will be collected prior to randomization:

1. Diabetes clinical
 - a. HbA1c
 - b. Total daily dose of insulin (mean of previous 7 days)
 - c. Severe hypoglycaemia in the run-in period
 - d. Diabetic ketoacidosis in the run-in period
 - e. Hospital admissions in the run-in period
2. Review carbohydrate (CHO) counting and offer dietetic support if needed
3. Pump upload and review of settings
4. Review of hypoglycaemia/hyperglycaemia management.

The control group will continue on their insulin pump therapy with or without CGM. They will attend the 3-monthly regular clinic appointments.

The intervention group will use the study device with the compatible CGM. They will attend additional visits required for device training and to review the pump settings. They will continue to attend their 3-monthly clinic appointments.

If needed, Visit 3 and 4A can be combined for intervention group.

VISIT 4 (Only for participants randomised to AHCL arm)

The additional visits for the HCL group are for device training to support the use of HCL.

Visit 4A: Pump training (2 hours)

Parents will be trained on how to use the Medtronic 780G insulin pump. They will be provided with a compatible meter (which communicates with the pump) along with the glucose strips for the study.

Visit 4B: CGM training (2 hours)

They will be instructed on how to link CGM on the Medtronic 780G pump and issued with compatible next generation sensor and transmitter, as well as CGM user guide. Initial low and high alarms will be set at 4.0mmol/L and 15mmol/L respectively, although these can be changed according to individual preference. Sensor naïve individuals will have familiarisation phase of 7 to 10 days to get used to wearing a sensor.

Visit 4A and 4B could be combined for participants familiar with sensors.

Visit 4C: Commencement of AHCL (1-2 hours)

Once CGM data has been established for a minimum of 3 to 7 days, participant returns for face-to-face instruction on AHCL use and initiation of 'SmartGuard'. During this visit, the sensor will be replaced to demonstrate sensor warm up and AHCL initiation, and provide an opportunity for those unfamiliar with CGM use to practice a sensor change with supervision.

Participants will subsequently have weekly communication via phone call or email for support for the following 4 weeks, and upload their pump weekly. Investigators will log all time spent training and in communication with participant. Communication can be more often – as per clinical need, and logged.

Visit 4D: Review of AHCL (after 4 weeks from commencement of AHCL, 1 hour)

Face-to-face meeting to upload insulin pump, review CareLink reports and revise settings (CHO ratio and Insulin action time)

Participants will be issued with enough consumables for the study.

Research staff will review CGM data at 8 weeks' with participants encouraged to contact the team if support/assistance required.

VISIT 5 (11 weeks after randomisation for control arm only)

Visit 5A: Insertion of blinded CGM: This constitutes first of the two sensors, each sensor provides data for 7 days. Parents will be instructed to test their children for a minimum 3 to 4x/day using the study meter.

Visit 5B: Insertion of 2nd blinded CGM: Participants will return 7 days after sensor insertion to remove and download the first week of CGM data. The study meter will be uploaded. A new sensor will be inserted and a fresh transmitter attached.

A total of 2 weeks of blinded sensor is required with at least 10 days of data. In participants who do not meet this requirement, repeat sensors will be offered till a maximum of 4 attempts of data collection

Visit 5C: Insertion of 3rd blinded sensor (if applicable)

Visit 5D Insertion of 4th blinded sensor (if applicable)

VISIT 6 (1 week after last blinded sensor) **End of RCT Phase**

The following data will be collected:

1. Auxological
 - a. Height
 - b. Weight
 - c. BMI
2. Diabetes clinical
 - a. HbA1c
 - b. Total daily dose of insulin (mean of previous 7 days)
 - c. Pump upload (for intervention group)
 - d. Severe hypoglycaemia since Visit 5 for Control arm / Visit 4d for Intervention arm
 - e. Diabetic ketoacidosis since Visit 5 for Control arm / Visit 4d for Intervention arm
 - f. Hospital admissions since Visit 5 for Control arm / Visit 4d for Intervention arm
3. Psychology measures: Psychological scales will be administered to parents on an electronic platform.
 - a. Functional health status: Quality of life (QOL) WHO 5, EQ5D
 - b. Fear of hypoglycaemia: Hypoglycaemia fear survey Parent
 - c. Diabetes-related distress: Problem Areas in Diabetes PAID-Parent version
 - d. Anxiety: GAD-7
 - e. Sleep quality: Pittsburgh Sleep Quality Index
 - f. Technology acceptance and satisfaction: DTQ
4. 24-hour food recall interview (to capture dietary pattern)
5. Parents of participants will be offered a semi-structured interview at the end of the study to share the lived experiences with use of new technology.

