4.3 Bias

4.4 Blinding and Randomisation

To minimise bias, participants will be allocated to treatment group based on minimisation. Blinding is not possible in this open label study and hence the maintenance of breaking codes is not required.

Minimisation will be used to allocate participants to study group based on the following balancing factors measured at baseline: age at Visit 1 (<6 years, 6 years and above), time in target range (<55%, greater or equal to 55%) collected from blinded sensor data, and study site. Minimisation is a method of ensuring excellent balance between groups for known prognostic factors(20). The Minimpy program (MinimPy)(19) will be used to allocate participants. Allocation will be undertaken by the delegated persons at Perth Children's Hospital.

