5.1 Source of Participants

Eligible participants will be identified through the Western Australian Children's Diabetes Database (WACDD) and state specific databases. A generic invite with the information sheet will be sent electronically. Participants will also be identified during their clinic visits. We may also use advertisements, notices, and/or media to recruit participants. Examples include flyers posted in public settings, newspaper ads, and radio and television advertisement. All advertisements and recruitment materials (e.g., video, audio, and telephone scripts) will be submitted to HREC for prior approval.

The inclusion and exclusion criteria are the same for both phases. Participants in the feasibility phase are permitted to participate in the RCT after a minimum wash-out period of 3 months.

5.2 Participant inclusion criteria.

1. Type 1 diabetes (diagnosis consistent with American Diabetes Association Classification of Diabetes Mellitus, diagnosed at least 1 year ago)
2. CSII therapy for at least 3 months
3. Age 2 to ≤ 7 years
4. HbA1c $\leq 8.5\%$ in the last 3 months
5. Total daily insulin of ≥ 8 units/day for the last two weeks
6. Participant and parent willing to follow study instructions
7. Living in an area with internet and cellular coverage

5.3 Participant exclusion criteria.

1. Commenced CGM in the 3 months prior to screening visit
2. Using advanced hybrid closed loop system: Control IQ
3. Uncontrolled coeliac disease
4. Uncontrolled thyroid disease
5. Inability or unwillingness to meet protocol requirements
6. Unwilling to perform 3 to 4 finger stick blood glucose measurements daily
7. Use of Hydroxyurea medication
8. Poor vision (of primary caregiver) precluding the use of investigational technology

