9.2 Sample Size

The feasibility phase aims to recruit 12 participants. This number has been selected as it will allow sufficient participants to be enrolled to familiarise the study team with the device and identify any major difficulties that may be encountered within the protocol in the larger RCT.

The power calculation for the RCT is for a parallel study design with two groups of equal size. Based on CGM data in this age group (8, 9) we would expect control group to spend on average 55% of TIR with SD 11.5. With alpha set at 0.05, 31 participants would be required per group to have 80% power to detect an increase of 8% points. It is assumed the total dropout rate will be up to 10% based on previous studies, so we plan to recruit 70 participants in total.

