Thank you for giving us your time and effort in taking part in this study. Your opinions about using diabetes technology are very valuable to us and we hope that you can now help us learn how this has affected your daily life with diabetes. Below you will see some statements about different kinds of diabetes treatments that include using different diabetes devices such as a blood glucose meter, insulin pump, continuous glucose monitor or closed loop insulin delivery system.

Please tick the box below that lists the diabetes devices you are using now as part of treatment. If you aren't sure, ask the diabetes nurse to help you.

- Glucose Meter(s) and daily use of an insulin pump
- Glucose Meter(s) and a Continuous Glucose Monitor (Medtronic, Dexcom or Libre) and daily use of an insulin pump

For those completing a follow-up study visit: Now we'd like to ask you some questions about the treatment approach that you selected above. We've listed below some parts of living with diabetes that might be made better or worse by your use of diabetes devices. For each of these, please circle the number that best tells how much of a problem it is now and then circle the number that best tells how it has changed for you compared to the treatment received before you entered this study.

	Is this a problem now?					How has it changed compared to your treatment before the study?				
	Very Much		Just A Little		Not At All	Much Worse	A Little Worse	Same	A Little Better	Much Better
1. Worry or fear about high blood sugar	1	2	3	4	5	1	2	3	4	5
2. Effort to keep low blood sugar from happening	1	2	3	4	5	1	2	3	4	5
3. Worry or fear about low blood sugar during sleep	1	2	3	4	5	1	2	3	4	5
4. Feeling different from others	1	2	3	4	5	1	2	3	4	5
5. Amount of time spent thinking about diabetes	1	2	3	4	5	1	2	3	4	5
6. Not knowing how eating affects blood sugar	1	2	3	4	5	1	2	3	4	5
7. Amount of time and effort needed for diabetes from my family or me	1	2	3	4	5	1	2	3	4	5

	Is this a problem now?					How has it changed compared to your treatment before the study?				
	Very Much		Just A Little		Not At All	Much Worse	A Little Worse	Same	A Little Better	Much Better
8. Worry or fear about long term health	1	2	3	4	5	1	2	3	4	5
9. Worry or fear about daytime low blood sugar	1	2	3	4	5	1	2	3	4	5
10. Effort to keep high blood sugar from happening	1	2	3	4	5	1	2	3	4	5
11. Pain or discomfort from finger sticks or monitors	1	2	3	4	5	1	2	3	4	5

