- 1) How do you feel your child's diabetes has affected your family or work life?
- 2) How do you think the HCL system could help with this
- 3) Do you feel comfortable sending your child to day-care / school?
- 4) Thinking about the support you received from the study diabetes Educator, how did you find the amount of contact? timing of contact? Would you have liked more/less/about the same amount of contact?

Technical issues

Did you encounter any device difficulties during the study? If so, can you explain them to me? -alarms; notifications; correction

Overall user satisfaction

How do you think your child managed with the system?

What was your knowledge / expectations of the system prior to starting the study?

How do you feel after completing the study?

Why did you enrol your child into the study?

Would you recommend this study/ system to others?

Feedback / questions for HyCLIP – final visit:

What were your expectations going into the study / were they met?

Tell us about your experience using the pump (both positive and negative):

- With sleep / exercise

- With food and insulin delivery

Did you get enough information when you started using the 780G insulin pump in Smart Guard?

Did you feel supported during the study? Did you mind the study staff monitoring your child?

Did you change your child's management during the day? During the night?

Are you confident using the system?

How long did it take you to trust the system?

How do you feel about going back to your old pump?

Did you notice any differences in your child's behaviour while he/she was in SmartGuard? And in what way?

How did you like using the pump?

(pick the face that matches how your child feels about the pump)

				
				
				

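### Re-entry of feasibility-phase families mixes first-time and second-time 780G users in the AHCL-arm training-time and device-interaction results, and the plan does not separate them

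*Protocol*

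**What the plan says.** Re-entry is allowed in Protocol 5.1: "Participants in the feasibility phase are permitted to participate in the RCT after a minimum wash-out period of 3 months". The wash-out paragraph in 4.2 explains the interval only by glycaemia: "The 3-month period is chosen to minimise the impact of any carry over of glycaemic impact with AHCL into the larger RCT".

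The earlier exposure is to the device that the RCT tests. In the feasibility phase (4.2), "Parents will be trained on how to use the Medtronic 780G insulin pump", and a two-week run-in in Manual Mode is "followed by a 6-week study phase (± 1 week) during which SmartGuard is enabled", with weekly staff contact. Section 9.2 sets the size of that phase: "The feasibility phase aims to recruit 12 participants".

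In the RCT, section 4.4 says "Minimisation will be used to allocate participants to study group based on the following balancing factors measured at baseline"; the factors are age, baseline time in range and site. The ANCOVA in 9.1 adjusts for the baseline value and those factors, and continuous psychosocial outcomes follow the same model. Prior feasibility participation appears in neither place. It is not an exclusion in 5.3 and is not among the RCT Visit 1 items in 4.2.

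The RCT secondary endpoints (4.1) include staff time on training, education and support as a health-economic item, and participants' interaction with and adherence to AHCL under human factors. Section 4.2 (Visit 4C) has investigators log all training and communication time.

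**The concern.** Three months without the device may be enough for a glycaemic effect to fade. It is not obviously enough for a parent to forget how to run the pump, how far to trust it, or what to expect of it. The sponsor regards such reactions as worth recording: the feasibility feedback form in the appendices asks "How do you feel about going back to your old pump" and how long it took to trust the system.

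The consequence depends on the type of outcome. A comparison between randomised arms is protected in expectation, because prior use is fixed before allocation. A summary of what it takes to train families on AHCL, or of how they interact with it, has no such protection. It is a description of one arm, and second-time users pull it towards less training and more practised use. The control arm has no device-training visits, so a shortfall in AHCL training time passes directly into the incremental cost used for secondary aim 4. Secondary aim 5, on user interactions, would describe a mixed group without saying so.

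**Working it through.** **Inputs from the Protocol.** Feasibility target 12; RCT total 70 in two equal groups, so 35 per arm (all in 9.2). No re-entry rate, training-time figure or parent-scale SD is given, so these are assumed below and shown as ranges.

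**The plan's own figures.** For 8 points, SD 11.5, two-sided alpha 0.05 and 80% power, the normal formula gives n = 2 × [11.5 × (1.960 + 0.842) / 8]² = 32.4 per group, against 31 stated; power at 31 is 78.2%. Allowing for dropout, 62 / 0.9 = 68.9, so 69 against 70 planned. These agree closely enough. They supply the denominator and otherwise do not bear on this point.

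**Share of experienced families.** With m re-entrants and equal allocation, the expected share of the AHCL arm is (m/2)/35 = m/70.
- m = 12, the ceiling: 12/70 = 17.1%
- m = 6, if half return: 6/70 = 8.6%
- m = 0: no effect

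**Training time.** If device-naive families need mean time T and re-entrants need (1 − r)T, the arm mean is T(1 − s·r), where s is the re-entrant share. The understatement is s × r:
- s = 8.6%, r = 50%: 4.3%
- s = 8.6%, r = 100%: 8.6%
- s = 17.1%, r = 50%: 8.6%
- s = 17.1%, r = 100%: 17.1%

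The range is therefore about 4% to 17%. Balance between arms does not change it, because a perfectly even split of 12 still places 6 experienced families among 35.

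**Parent scales.** Here only an uneven split matters. Treating allocation as unrelated to prior use (hypergeometric: 70 children, m re-entrants, 35 per arm, two-sided):
- m = 12: 8:4 or worse 0.342; 9:3 or worse 0.110; 10:2 or worse 0.023
- m = 6: 5:1 or worse 0.198; 6:0 0.025

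An 8:4 split is a difference of 4 families, or 4/35 = 0.114 of an arm. If experience shifts a score by 0.5 to 1 SD (assumed), the group difference moves by 0.5 × 0.114 = 0.06 SD to 1 × 0.114 = 0.11 SD. The standard error with 35 per arm, before baseline adjustment, is √(2/35) = 0.24 SD. The shift is under half of one standard error.

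**The case against.** A reader might infer that re-entry biases the comparison between arms, since families who liked the device are the likeliest to return. The documents do not support that. Selective return decides who enters the RCT, not which arm they join, so no difference in prior use is expected between arms. Chance imbalance in an unlisted factor is already reflected in the confidence interval. The parent scales are also re-measured at RCT Visit 1 and adjusted for baseline, and site is a minimisation factor, which would give some indirect balance if the feasibility phase ran at one site (not stated). Section 9.1 declares the secondary outcomes exploratory. All of this stands. What remains for the parent scales is effect modification, or a reaction after allocation by experienced families assigned to control, which baseline adjustment cannot remove.

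It is also fair that 12 is a ceiling: returning families must be willing and must meet the entry criteria again. Visits 4A to 4D have stated lengths, which limits how far training time can fall, so the 100% reduction is an outer bound. Training time is one of seven health-economic items.

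The DTQ follow-up, which asks "how it has changed for you compared to the treatment received before you entered this study", could be called ambiguous for re-entrants. The phases have separate consents (section 12) and a gap of at least 3 months, so therapy at RCT entry is the natural reading, and the questionnaire also scores current problems separately. This adds little.

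Lastly, a sensitivity analysis may sit in an analysis plan that is not shown. The re-entry rule, its rationale and the baseline data items, however, are fixed in the Protocol, and none of them takes prior device use into account.

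**Conclusion.** The point holds in a limited form. Re-entry after a wash-out justified only by glycaemia means that AHCL-arm training time and technology-interaction results may mix first-time and second-time users, whatever the balance between arms. The size is 0 to 12 of 70 families. Under the assumptions of 8.6% to 17.1% re-entrants and 50% to 100% less training, mean training time is understated by about 4% to 17%, in the direction that favours AHCL on cost. If nobody re-entered, the problem disappears.

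For the exploratory parent scales the effect is small: 0.06 to 0.11 SD with an 8:4 split and an assumed 0.5 to 1 SD shift, against a standard error of about 0.24 SD. The lack of a minimisation factor for prior use is not the cause of the training-time and human-factor problem, and adding one would not cure it. The primary time-in-range result is not called into question.

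**What to change.** - Record for each RCT child whether the family took part in the feasibility phase, and report the number by arm.
- Report training and support time and the human-factor results for device-naive AHCL families as the main result, with the all-participant result alongside. Carry both training-time figures into the cost-effectiveness calculation.
- Add prior participation (yes/no) as a covariate in the psychosocial ANCOVA, with a sensitivity analysis that excludes re-entrants.
- Leave the minimisation scheme unchanged. The Protocol version is dated November 2022 and the trial is due to finish in May 2023, so a new factor would reach only late entrants and would alter allocation mid-trial for the sake of exploratory endpoints.

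The cost is one data item, one covariate, a little more analysis, and a slightly smaller sample for the descriptive AHCL-arm results: with 12 re-entrants evenly split, 35 − 6 = 29 families instead of 35. Recruitment and the primary analysis are untouched.

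### The protocol contradicts itself on whether every child attends Visit 2B, the only visit that collects baseline diet

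*Protocol*

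**What the plan says.** All of the following is in Protocol section 4.2, RCT phase, unless stated otherwise.

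- **Baseline recall.** Visit 2B has three items. The first is "The blinded sensor is removed". The second is "Insertion of 3rd blinded sensor (if applicable) and to be removed a week later". The third is "24-hour food recall interview (to capture baseline dietary pattern". No other visit before randomisation (1, 2A, 2C or 3) lists a food recall.
- **Figure 2 note.** "Visits 2B,2C, 5C, 5D optional if data requirement from blinded CGM not met".
- **Visit 2A text.** The data rule is "A total of 2 weeks of blinded sensor is required with at least 10 days of data". For children who miss it or lose a sensor, "repeat sensors will be offered till a maximum of 4 attempts of data collection (2B, 2C". The text then gives the run-in length: "Hence, the run-in period duration will be over 2 to 4 weeks".
- **End of study.** Visit 6 lists "24-hour food recall interview (to capture dietary pattern", with no restriction by arm.
- **Use.** Section 3 makes the relation between dietary intake and AHCL use a secondary aim of the RCT. Section 4.1 defines secondary endpoint 3 from the 24-hour recall. Section 9.1 says that effectiveness is assessed from baseline and Visit 6 data.

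**The concern.** A one-time baseline measurement sits inside a visit that two places in the protocol treat as contingent on sensor trouble. If a site takes those two places at their word, a child whose first two sensors met the data rule goes from the second sensor to Visit 3 without a recall.

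Three things would then be at stake.

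- The gap cannot be closed later. Visit 3 includes a carbohydrate-counting review and an offer of dietetic support, and the intervention arm then starts a system that may change how families manage food.
- The gap would not be random. Children with a baseline recall would be those whose sensors failed or fell off, which may go with age, behaviour or family routine.
- Four centres run the RCT. If they read the text differently, the availability of baseline diet would also vary by site.

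**Working it through.** The protocol gives no figure to reproduce here. The check sets the passages side by side and counts the days of the run-in.

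**1. Who attends Visit 2B?**

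| Place in section 4.2 | Status of Visit 2B |
|---|---|
| Figure 2 note | Optional, tied to the blinded-CGM data requirement |
| Visit 2A text | Named, with 2C, as a repeat-sensor attempt |
| Visit 2B, item 1 (sensor removal) | No condition |
| Visit 2B, item 2 (third sensor) | Conditional |
| Visit 2B, item 3 (food recall) | No condition |

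The first two rows make the visit contingent. The 2B list makes only one of its three items contingent.

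**2. Day count for a child whose first two sensors work.**

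- Sensor 1 goes in at Visit 1: day 0.
- Sensor 2 goes in at Visit 2A: day 0 + 7 = day 7.
- Sensor 2 comes off after 7 more days: day 7 + 7 = day 14, the 2-week lower end of the run-in.

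One sensor gives 7 days, which is below the 10 required, so every child needs a second sensor. It must also be read before allocation, because section 4.4 uses time in range from the blinded sensor as a minimisation factor. Some contact at about day 14 is therefore unavoidable. Visit 2B is the only listed visit that removes this sensor.

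**3. Does that settle that everyone attends 2B?** No. The note groups 2B with 2C, 5C and 5D, and each of those three consists only of an optional sensor insertion. The control arm's closing sequence also shows that the protocol does not always list a removal visit: if 5C is not needed, the next listed visit after 5B is Visit 6, set one week after the last blinded sensor. A site could likewise take sensor 2 off when the family comes for Visit 3 and regard 2B as skipped.

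**4. How many children?** Let N be the number randomised (70 planned, section 9.2), f the fraction of them at sites that follow the note, and s the fraction of those children whose first two sensors sufficed. Then

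baseline recalls lost = N × f × s.

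The documents give neither f nor s. If every site follows the 2B list, f = 0 and the loss is 70 × 0 × s = 0. If every site follows the note, f = 1 and the loss is 70 × s, with s unknown.

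**The case against.** The strongest defence is that the 2B list is the operative text and plainly describes a visit for every child. It begins with a removal that every child wearing the second sensor needs. It marks only the third sensor as conditional, a qualifier that would be largely redundant if the visit took place only after sensor failure. In the ordinary case, whether the data rule was met is known only once sensor 2 is off. The note is loosely worded: read literally, it makes visits optional when data are insufficient. The figure itself is not visible in the text available, so what the note attaches to cannot be checked. The intended meaning may be only that the extra sensors are optional.

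Much of this stands. A reader might infer that children with two working sensors would have no baseline recall, or that baseline diet would exist only where sensors failed. The documents do not support either statement, because both require the note to override the visit list. A reader might also put a number on it: assuming that 20–40% of children need a third sensor, 60–80% of 70, or 42 to 56 children, would lack a baseline. That range has no anchor in the protocol and also assumes that every site follows the note.

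The defence is also right on impact. Endpoint 3 is a proportion of children meeting dietary recommendations. Section 9.1 names glycaemic, auxological, clinical and psychosocial outcomes for ANCOVA and does not name diet, so the protocol specifies no baseline-adjusted dietary model.

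What the defence does not remove is the contradiction. The note calls 2B optional, the Visit 2A text supports that reading, and no other visit would catch a missed recall.

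**Conclusion.** The point holds as an internal contradiction with a possible loss of data. Section 4.2 does not settle whether every child attends the one visit that records baseline diet. Depending on which text a site follows, a child whose first two sensors sufficed either has a baseline recall or has none. The size runs from no loss upward and cannot be fixed from the documents.

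The reach is narrow. Only the dietary aim and endpoint are affected, and section 9.1 declares secondary outcomes exploratory. Because Visit 6 repeats the recall in both arms, the randomised comparison of diet at study end survives. What could be lost is the description of diet at entry, any adjustment for it, and any analysis of change. The primary endpoint is not involved. This is a minor point, but more than a clerical one, since the data cannot be collected after allocation.

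**What to change.** Reconcile the passages in one of two ways.

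1. Take Visit 2B out of the optional list in the Figure 2 note and state that every child attends it, so that only the third and fourth sensor insertions are optional. Adjust the label in the Visit 2A text to match.
2. Move the baseline recall to a visit that every child attends before randomisation. Visit 3 would serve, provided that the recall comes before the carbohydrate-counting review, the offer of dietetic support and the allocation. Visit 3 may be combined with the two-hour Visit 4A in the intervention group, so the order within the day should be written down.

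The first option keeps closest to the existing 2B list. Either is an edit of a line or two and adds no procedure. If recruitment has already begun, each site should also record which reading it has followed, so that missing baseline recalls can be reported by site and by sensor outcome.
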